The secondary objectives for this study are to assess the potential association between the occurrence of predefined and newly identified AESIs and vaccination with Ad26.COV2.S in the following specific subpopulations (part of the main study population):

- Immunocompromised individuals,
- Pregnant women,
- Individuals who have a prior history of thrombotic events and/or thrombocytopenia,
- Prior SARS-CoV-2 (COVID-19) infection,
- Individuals with a prior history (ever) of the specific event more than a year before start of follow-up.

These results will be compared to COVID-19 vaccine unexposed individuals and, to individuals exposed to other types of COVID-19 vaccines (mRNA or adenovirus-based platforms) or compared to a control window within the same individual.

Endpoints

Feasibility Assessment

The endpoints for the feasibility assessment, including a monitoring phase, are:

- Quality assessment of data that has been extracted from the source data banks (completeness, logic and benchmarking between data sources and against external data)
- The number of doses and uptake of different COVID-19 vaccines by calendar time
- The demographic and morbidity characteristics of individuals receiving different COVID-19 vaccines
- Algorithms for AESI identification (including exacerbation of asthma)
- Incident rates and cumulative incidence (risk) of the selected AESIs and corresponding 95% confidence intervals (CIs), without prespecified risk windows

- Risk factors for AESI.

Safety Evaluation Study

The primary endpoints for the safety evaluation study are to estimate the risk of the selected AESIs listed below among individuals vaccinated with the Ad26.COVS.S vaccine and in corresponding unexposed individuals and individuals exposed to other types of COVID-19 vaccines (split between mRNA platform-based vaccines and adenovirus-based platforms), or during a control window within the same individual.

The contractual agreements with data partners will stipulate the ability to allow newly identified AESIs to be incorporated into the study objectives, and the current protocol that will be used for governance approvals will state that additional AESI may be added. Each data access provider is responsible to inform the appropriate ethics boards of these amendments.

Acute events (events expected to be recorded within 60 days of vaccination).

- The incidence of anaphylaxis within 0-2 days.

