8.1.2.1. Self-controlled Risk Interval Design (Primary Study Design for Acute Events)

The SCRI design will compare the risk of the AESI in a post-vaccination risk window to a pre-vaccination control window (sensitivity analysis) and post-vaccination control window (main analysis) within the same individual.

The SCRI design will include only individuals in the primary analysis who received at least one first-ever dose of the Ad26.COV2.S vaccine during the study period. Vaccinated individuals enter the study at the date of the start of the pre-vaccination control window. The SCRI design will compare the risk of each outcome during the post-vaccination risk window following the COVID-19 dose with a self-matched control interval that may be prior to vaccination, or after the vaccination risk window, to assess the baseline risk of the outcome. The control window will have the same maximum length as the risk window to minimise time-varying confounding that cannot be measured. In case the follow-up time does not capture the maximum post-vaccination risk or control window due to right censoring, all available follow-up time will be utilized. Follow-up will be censored upon vaccination with another COVID-19 vaccine or end of follow-up. A washout period between the control and risk window will be applied to minimise capturing of prevalent events during the risk window. A post-vaccination control window may induce a bias towards the null when an AESI that was identified during the vaccination risk window, is captured again during the control window due to a re-admission instead of reoccurrence of the AESI. This situation is more likely to be encountered for acute potentially recurring events such as cardiac events (including acute coronary syndrome, myocarditis, pericarditis, arrhythmia, and stress cardiomyopathy). Moreover, due to lag-times in updating the relevant databanks, there is a higher risk that the post-vaccination control window may not capture all events and underestimate the rate of events. Use of a pre-vaccination control window will deal with these issues. In a sensitivity analyses, we will use a pre-vaccination control window and a post-vaccination control window will be used for the main analysis. In a sensitivity analysis, vaccination to other non-COVID-19 vaccines will also be an exclusion and censoring event.

We will also compare the Ad26.COV2.S vaccine with active comparators with 1) only 1-dose strategy and 2) a 2-dose strategy.

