8.3.4. Covariate Definition

Feasibility Assessment

In the feasibility assessment, covariates will be assessed at the time of COVID-19 vaccine administration or time-matched non-vaccinated individuals.

Safety Evaluation Study

Covariate assessment for the description of the patient population at baseline (index date) will use all available time of enrolment in the corresponding data source (minimum required enrolment period is 1 year).

Covariates will be assessed at index date (for the cohort design) to define patient populations of special interest or priority vaccination groups, to define subgroups of interest for sensitivity analyses, or to control for confounding.

We will consider the following time-varying covariates and corresponding period of evaluation for the SCRI measured at start of the risk window and the control window. To capture use of medications of interest during the month prior to start of the study periods (i.e., risk control and control risk), we will consider the drug supply covering the month prior to the start of the two periods of interest.

- Analgesics (month prior)
- Antibiotics (month prior)
- Antiviral medications (month prior)
- Systemic Corticosteroids (month prior)
- Immunosuppressant therapy (month prior)
- Non-steroidal anti-inflammatory drugs (month prior)
- Heparin (month prior)
- Novel oral anticoagulants (month prior)
- Warfarin (month prior)
- Aspirin (month prior)
- Influenza vaccine (month prior)
- Any pneumococcal vaccine (month prior)
- Any herpes zoster vaccine (month prior)

-
- Human papillomavirus vaccine (month prior)
 - Meningitis vaccine (month prior)
 - Pregnancy (at start of each window of interest)
 - COVID-19 infection (month prior)

For the cohort design, covariate status for all time-varying factors will be measured at index date. All covariates will be assessed in specific periods. For the secondary analysis in dedicated subgroups or patients with a past history, any time prior as the look-back period for the assessment of the covariates will be used, reference point is index date. For vaccinations other than COVID-19, follow-up time will be censored in a sensitivity analysis.

Population characteristics will be identified based on diagnoses, medicines, laboratory data, survey observation or medical observations, and observation period information.

Demographic characteristics

- Age
- Sex
- Pregnancy

Pregnancy status and pregnancy trimester at index date.

- Frailty

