8.7.1.3. Self-controlled Risk Interval Design**Descriptive Statistics**

The number of cases of each AESI will be reported in the control and risk windows, overall and by important covariates.

Measures of Association

Conditional Poisson regression will be used to estimate incidence rate ratios and 95% confidence intervals (CIs). The SCRI inherently adjusts for both measured and unmeasured time-constant factors such as sex and chronic health conditions with onset before the start of follow-up. Time-varying confounders (e.g., medications and other vaccinations) may be included as covariates in regression models. Subgroup analyses will be conducted by groups defined by demographic and clinical characteristics and other covariates of interest.

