8.7.3. Secondary Analyses

Analyses within the primary study designs (cohort design for non-acute events and SCRI design for acute events) will be conducted for sub-populations:

- Immunocompromised individuals,
- Pregnant women,
- Individuals who have a prior history of thrombotic events and/or thrombocytopenia,
- Prior COVID-19 infection (yes/no),
- Individuals with a prior history (ever) of the specific event more than a year before start of follow-up.

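### In pregnant women the main SCRI control window always lies later in gestation or after delivery, and an optional pregnancy status read only at window start leaves part of that change in baseline risk in the vaccine IRR

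*Protocol*

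**What the plan says.** Pregnant women are listed as a subpopulation in the secondary objectives (Abstract and section 7) and again in section 8.7.3 ("Pregnant women"). The comparators named for these subpopulations are unexposed people, recipients of other COVID-19 vaccines, "or compared to a control window within the same individual". Section 8.7.3 settles the design: "Analyses within the primary study designs (cohort design for non-acute events and SCRI design for acute events) will be conducted for sub-populations". Table 5 repeats this.

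In section 8.1.2.1 the risk window is compared with a "post-vaccination control window (main analysis) within the same individual". On length: "The control window will have the same maximum length as the risk window". Section 8.1.3 adds a buffer whose length is left to the SAP. The events that end SCRI follow-up (section 8.2.3) do not include the end of pregnancy.

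Section 8.3.4 lists among the SCRI time-varying covariates "Pregnancy (at start of each window of interest"). In the demographic list it gives "Pregnancy status and pregnancy trimester at index date". Section 8.7.1.3 says: "Time-varying confounders (e.g., medications and other vaccinations) may be included as covariates in regression models". Section 8.9 does not discuss gestational or postpartum change in risk.

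**The concern.** A self-controlled comparison removes only what stays constant within a person. Gestation moves one way, so among women pregnant at vaccination the main control window is never at the same stage of pregnancy as the risk window. If the baseline rate of an event differs between trimesters, or between pregnancy and the weeks after delivery, that difference enters the vaccine IRR unless the model carries it.

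The protocol's covariate carries only part of it. A status read once at the start of a window cannot register a delivery or a trimester change within that window. Trimester at index is a constant for each woman and drops out of a conditional model. Even the status covariate is optional.

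The events most exposed are those whose rate rises after delivery. An inflated control window pulls the IRR down, so a real excess could look smaller or absent in a subgroup the protocol chose to examine. Section 6.1 records a product warning about rare clotting events in women aged 18 to 49, so the thrombotic outcomes are not a side issue here.

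**Working it through.** **The protocol's own SCRI figures.** The protocol gives no figure for this point. Its SCRI case numbers for 80% power (Table 4: 195, 69, 41, 29) are not in dispute. With equal windows, p = RR/(1+RR) and two-sided alpha 0.05, n = [(1.96 × 0.5 + 0.842 × √(p(1−p)))/(p − 0.5)]² gives 194, 69, 41, 29.

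**Inputs from the protocol.** Risk window of 1–28 days for thrombotic events (Table 1); control window after it and of equal maximum length; no end of follow-up at delivery.

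**Assumptions not in the protocol.** Time from vaccination to delivery is uniform over 0–280 days, the buffer is 14 days, risk is flat during pregnancy, the postpartum rate is k times the pregnancy rate, and the true vaccine IRR is 1. The control window is then days 43–70.

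**Status covariate included.** Women pregnant at the start of the risk window but not of the control window inform only the status coefficient. The IRR therefore comes from women still pregnant at the start of the control window, who have 280 − 42 = 238 possible delivery days. Their risk window contains no postpartum time. Those delivering within the 28-day control window contribute on average half of it as postpartum time, a share of (28/238) × 0.5 = 0.0588. The apparent IRR is 1/[1 + 0.0588(k − 1)].

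**Unadjusted.** The postpartum share of the risk window is 14/280 = 5%. If the excess lasts 42 days, its share of the control window is 42/280 = 15%, and the apparent IRR is [1 + 0.05(k − 1)]/[1 + 0.15(k − 1)]. If it lasts through the window, the share is 56/280 = 20%, and the apparent IRR is [1 + 0.05(k − 1)]/[1 + 0.20(k − 1)].

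| Apparent IRR, true value 1 | k = 2 | k = 3 | k = 5 | k = 10 |
|---|---|---|---|---|
| Status at window start included | 0.94 | 0.89 | 0.81 | 0.65 |
| Unadjusted, excess lasts 42 days | 0.91 | 0.85 | 0.75 | 0.62 |
| Unadjusted, excess lasts through the window | 0.88 | 0.79 | 0.67 | 0.52 |

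**Window length.** With the status covariate, windows of length L and a 14-day buffer, the postpartum share is (L/2)/(280 − L − 14).
- 14-day windows: 7/252 = 0.0278, giving 0.97, 0.95, 0.90, 0.80.
- 42-day windows: 21/224 = 0.0938, giving 0.91, 0.84, 0.73, 0.54.
- The three-day anaphylaxis window: 1.5/263 = 0.0057, giving 0.99 to 0.95.

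The bias is therefore small for short windows only if the covariate is used. Unadjusted 14-day windows with a 14-day buffer read 0.91, 0.73 and 0.58 at k = 2, 5 and 10.

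**Direction.** Take 60-day windows, vaccination in the last 84 days of pregnancy, a 42-day postpartum excess and no adjustment. The apparent IRR is 0.97 to 0.92 with no buffer, about 1.05 to 1.2 with a 14-day buffer, and about 1.2 to 1.75 with a 28-day buffer (k = 2 to 10). Here the risk window holds much of the postpartum excess and the control window can begin after it has ended.

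**The case against.** Several counter-arguments carry weight.

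- Section 8.3.4 lists pregnancy as an SCRI covariate, so unadjusted figures do not describe the analysis most likely to be run. This stands, and the adjusted row is the one to rely on. The residual is smaller but not negligible.
- The protocol does not call the covariate yes/no. Section 8.3.4 also says that time-varying factors are measured at the start of both windows, so trimester at each start is not excluded. That is fair, but it would still miss change inside a window, and the only place where trimester is specified is the index date.
- Covariate detail belongs to the SAP. This is true of detail in general. Here, however, the protocol itself fixes when pregnancy is measured and makes adjustment optional.
- Other analyses offer a check: both window orders are run, and section 8.7.2.1 matches the cohorts on pregnancy status. However, the acute-event cohort is a sensitivity analysis, section 8.7.3 keeps subpopulation work within the primary designs, the matching list in section 8.1.2.2 omits pregnancy, and no list includes trimester.

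A reader might infer that the main analysis is always biased downwards and the pre-vaccination version upwards, so that the two bracket the truth. The documents do not support that. The 60-day case can vanish or reverse, and a pre-vaccination window reaches back to earlier gestation or before conception, which is a different bias of unknown sign.

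**Conclusion.** The point holds as a fault in a stated rule. Followed as written, the SCRI in pregnant women leaves within-window gestational and postpartum change in the vaccine IRR. With 28-day windows and the status covariate included, a null effect reads about 0.94 to 0.65 for k = 2 to 10. Leaving the covariate out gives 0.91 to 0.62 or 0.88 to 0.52, depending on how long the postpartum excess lasts. These sizes rest on assumed values of k, gestation at vaccination, buffer and postpartum duration; the protocol supplies none of them. When postpartum risk is the higher, the error is mostly below 1, but not for every window or every gestation.

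It would go too far to say that the subgroup result is uninterpretable, or that the primary SCRI in the whole vaccinated population is affected to this degree. The calculation concerns only women pregnant at vaccination, in a secondary analysis. It should be corrected before the final analysis.

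**What to change.** In sections 8.3.4, 8.7.1.3 and 8.7.3, for the pregnant subpopulation:

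- Split SCRI person-time and events at trimester boundaries and at the end of pregnancy.
- Include pregnancy state (first, second or third trimester, postpartum) as a required time-varying factor in place of the optional status at window start, and state how long the postpartum state lasts.
- Do not censor at delivery in the main analysis. An event may precipitate delivery, and section 8.2.4.2 requires follow-up in both windows. Censoring would therefore drop risk-window cases who deliver before the control window opens, which could itself hide harm.
- Report alongside it the matched cohort for acute events in pregnant women, matched on pregnancy status and trimester at index.

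The cost is analysis work, sparse strata and wider intervals. The analysis is also limited to data sources with usable pregnancy start and end dates. Trimester at index already requires gestational timing. A perinatal registry is described for VID (section 8.4.2) and for PHARMO (section 8.4.3), but the SIDIAP description (section 8.4.1) mentions none, so availability there must be confirmed first.

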Section 7 Research Question and Objectives	Minor editorial changes were made; Primary objective related to the safety evaluation study has been added; Booster dose assessment objective was added; AESI list has been reduced; Asthma Exacerbation was added as an endpoint; Prior COVID-19 was added as a matching variable.	This was not described in the previous version. Since protocol development, the use of booster doses in recipients of the first dose of Ad26.COVS.S has been approved. 17 AESI were prioritised by the Sponsor for the first feasibility report. Prior COVID-19 infection is an important confounder for most of the studied AESIs.

Protocol section	Brief description of the change	Reason
Section 8.2.1 Study setting, Section 8.4.4 Data sources/ARS, Section 8.8.8 Quality Control/ARS	ARS Toscana (IT) cannot participate in the study until further notice	Due to the ongoing revision of the procedure for data access in the Tuscany Region, ARS must suspend its activities concerning the re-use of data until the revision is complete.
Section 8.1 Study Design	Index date is the time of COVID-19 vaccination (time zero), and the follow-up time is the start of each risk window	This has been clarified in the entire protocol in line with the statistical analysis plan (SAP).
Section 8.1 Study Design	Non-vaccinated individuals were removed from the feasibility assessment	Only vaccinated individuals are included.
Section 8.1.2.2 Cohort design	This section and its corresponding figure (figure 2) were updated according to the SAP	Giving an example of matched cohorts at the index date will clarify the methodology applied.
Section 8.2 Setting and study population	Updated	To reflect all protocol amendments and updates.
Section 8.2.3 Study duration and follow up	The study period start date was changed from 01 December 2020 to the date when vaccination with Ad26.COV2.S began in each country	To have alignment in calendar time for each of the vaccines.
Section 8.2.1 Study setting, Section 8.4.4 Data sources, Section 8.8.8 Quality Control	CPRD (UK), HSD (IT), and Norwegian Health Registers (NO) data sources were discontinued from the study	Capture of the use of the Ad26.COV2.S vaccine is very limited in the UK, in the HSD data source in Italy, and in Norway.
Section 8.2.4.3	Inclusion criteria in cohort design has been adapted according to the SAP	
Section 8.3 Variables	Updated	To reflect all protocol amendments and updates.

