Individuals in the Ad26.COV2.S exposed cohort will be individually matched to one individual in the concurrent unexposed cohort and to one individual in each active comparator cohorts on key clinical variables (exact age, sex, prior COVID-19 infection, and presence of one or more risk factors for severe COVID-19 (e.g., cancer, sickle cell disease, obesity, chronic kidney disease, chronic respiratory disease, human immunodeficiency virus infection), and month of vaccination (using calliper if needed)) at the index date. Additional details on the matching process will be specified in the statistical analysis plan (SAP). A single individual may contribute person-time to the exposed and unexposed groups at different time points (details will be described in the SAP). Individuals will be classified into exposure groups that are compatible with their data at the index date. Follow-up under unexposed status is censored if an individual receives a

COVID-19 vaccine. In a sensitivity analysis, vaccination to other non-COVID-19 vaccines will also be an exclusion and censoring event.

Setting and Study Population

For the implementation of the feasibility assessment, electronic health care databases in Southern and Western Europe that have shown interest and are a member of the Vaccine Monitoring Collaboration for Europe (VAC4EU) will be used. The selected data sources and two-letter country codes are as follows:

- SIDIAP (Sistema d'Informació per el Desenvolupament de la Investigació en Atenció Primària) [Information System for Research in Primary Care] (ES)
- VID, the Foundation for the Promotion of Health and Biomedical Research of Valencia Region [FISABIO] (ES)
- PHARMO DATABASE NETWORK (PHARMO Institute for Drug Outcomes Research) (NL)
- ARS Toscana (Agenzia Regionale di Sanità della Toscana) [a research institute of the Tuscany region of Italy] (IT)]. See section 8.2.1 regarding conditional participation of ARS Toscana.

When needed (based on specific safety concerns occurring in specific countries, or because of size) additional data sources may be added for dedicated evaluation studies, if they have adequate data on exposure, outcomes and covariates.

Feasibility Assessment

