The sponsor has created a list of AESIs based on current knowledge of the Ad26.COV2.S vaccine. Background incidence rates for most of the data sources and AESIs are available on the VAC4EU dashboard <https://vac4eu.org/covid-19-tool/>. Definitions and codes are available on Zenodo (<https://zenodo.org/communities/vac4eu/>).

Covariate definition

Feasibility Assessment

In the feasibility assessment, covariates will be assessed at the time of COVID-19 vaccine administration (index date).

Safety Evaluation Study

For the cohort analysis, covariates for the study populations will be defined at the index date. For the SCRI design, time-varying covariates will be identified both at the start of the risk window and the control window.

Covariates will be used to define and describe the study cohorts and populations of special interest and their baseline characteristics and/or to control for confounding. Additional covariates may be added during the conduct of the study if deemed important. The look-back observation period to define covariates of interest will be all available information before the index date in each data source with a minimum of 12 months, except when an alternative look-back window is specified.

Data Sources

The study will use data from secondary electronic health record databases that are population-based. All data sources will have the ability to provide data on COVID-19 vaccines, outcomes (diagnoses, procedures, laboratory results, and treatments), and important covariates. It is not currently known the extent to which COVID-19 vaccines, product types, and batch numbers will be captured in data sources. To be included in the study, data sources should preferably be updated at a minimum once every 3 months. At the proposal stage, members of VAC4EU were offered the option to participate in the study. Four data sources from 3 countries (Spain, the Netherlands and Italy) will be included in the study. A more detailed description will be included in the VAC4EU FAIR Catalogue.

When establishing the agreements with the data sources to conduct the study, it will be emphasized that the current list of AESIs may be expanded during the course of the study to accommodate newly identified AESIs.

Study Size

The study will be conducted in a source population of approximately 18.1 million individuals, although children will not be vaccinated. It is assumed that up to 10% will be vaccinated with the Ad26.COV2.S vaccine.

Main Statistical Methods

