The eFI frailty score as described by Clegg et al ([Clegg 2016](#)) with a count of the number of different conditions will be created. Details will be available in the SAP.

Comorbidities (any time prior)

- Cancer (other than non-melanoma skin cancer)
- Chronic kidney disease (exclusion for acute kidney injury)
- Acute coronary syndrome (exclusion for cardiac/cardiovascular events)
- Chronic respiratory disease (chronic obstructive pulmonary disease, asthma)
- Obesity
- Down's syndrome
- Type 1 (excluded for type 1 when AESI) or type 2 diabetes
- Prior thrombosis (exclusion for thrombosis as outcome – see [Table 1](#))
- Morbidity index: number of different ATC codes (Level 5) dispensed in the year prior to cohort entry
- History of anaphylaxis
- History of any type of allergic reaction
- Immunocompromised conditions (will be used to define subgroups for secondary analyses)

-
- Immunodeficiencies
 - Systemic Immunosuppressant medication use
 - Human immunodeficiency virus and other immunosuppressing conditions
 - Parkinson’s disease
 - Stroke/brain injury
 - Dementia
 - Difficulty walking
 - Chronic use of home oxygen (>3 months of continuous use)
 - Palliative care
 - Heart failure (exclusion for heart failure as an outcome).

Covid-19 History

- Prior recorded COVID-19 infection as yes/no for the feasibility studies and by severity for the final study (non-hospitalised, hospitalised)

Comedication (dispensed/prescribed/used in period or episode covering this period)

- Analgesics (month prior)
- Antibiotics (month prior)
- Antiviral medications (month prior)
- Systemic Corticosteroids (month prior)
- Non-steroidal anti-inflammatory drugs (month prior)
- Psychotropics (year prior)
- HMG-CoA Reductase Inhibitors (statins) (year prior)
- Novel oral anticoagulants (month prior/time-varying)
- Warfarin (month prior)
- Aspirin (month prior)
- Oral contraceptives (year prior)
- Hormone replacement therapy (year prior)
- Heparin (month prior)
- Immunosuppressants
- Use of antihypertensive drugs.

Vaccinations

- Administration of any other COVID-19 vaccine from the reference date until the end of the follow-up period (censoring criterion)

-
- Influenza vaccine (month prior/time-varying)
 - Any pneumococcal vaccine (month prior/time-varying)
 - Any zoster vaccine (month prior/time-varying)
 - Human papillomavirus vaccine (month prior/time-varying)
 - Meningitis vaccine (month prior/time-varying).

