8.7.2. Main Statistical Methods

8.7.2.1. Matching

For the cohort designs, matching will be used to ensure comparability on observed covariates between groups to be compared. There will be a match on the following key variables at index date:

- Age (year of birth)
- Sex
- Pregnancy status
- Immunocompromised state
- Prior COVID-19 infection
- Calendar time (with calliper approach) Prior recorded COVID-19 infection (yes/no)
- Presence of one or more risk factors for severe COVID-19 (e.g., cancer, sickle cell disease, obesity, chronic kidney disease, chronic respiratory disease, human immunodeficiency virus infection).

For the SCRI design, an individual is matched with itself, and therefore analyses will be controlled for all stable variables.

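### The cohort matches on COVID-19 infection as ever/never, so a recently infected unvaccinated person can be paired with a vaccinee whose infection is old; this can bias the acute-AESI comparison with the unexposed downwards

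*Protocol*

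**What the plan says.** The abstract and section 8.1.2.2 match each Ad26.COV2.S recipient to one unexposed person on a short list that includes COVID-19 history: "exact age, sex, prior COVID-19 infection, and presence of one or more risk factors for severe COVID-19" in the abstract, with near-identical wording in 8.1.2.2. Neither place sets a time limit. Section 8.7.2.1 lists the variable twice, once giving its form: "Prior recorded COVID-19 infection (yes/no").

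The abstract sets the covariate look-back as "all available information before the index date in each data source with a minimum of 12 months", unless another window is specified. None is specified for COVID-19 history in the cohort. Section 8.3.4 refines that history by severity only: "Prior recorded COVID-19 infection as yes/no for the feasibility studies and by severity for the final study". For the SCRI, the same section lists COVID-19 infection in the prior month among the time-varying covariates.

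The exclusion criteria in 8.2.5 concern earlier COVID-19 vaccination and the AESI washout, not recent COVID-19. The unexposed index date must be a day without a COVID-19 vaccine dose, aligned in calendar time with the vaccinee; infection status on that day is not restricted.

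The reason given in section 3 for adding the matching variable is that "Prior COVID-19 infection is an important confounder for most of the studied AESIs".

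**The concern.** Matching on ever/never infection balances the proportion with any recorded infection, but not how recent it was. The protocol itself treats recency as relevant: the SCRI list uses the prior month, and section 8.9 describes infections as time-varying risk factors for most acute events that most of the data sources can capture.

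If acute infection raises AESI risk for some weeks, and recently infected people are more common among the unexposed than among vaccinees, infection-related events accumulate in the unexposed arm and the IRR falls.

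The analysis most exposed is the acute-AESI cohort. Section 8.1.3 adds it because the SCRI may be confounded by time-varying factors, and names seasonality as a proxy for respiratory infections. A check meant to guard against infection-related confounding should not use a key that cannot tell a current infection from an old one. A falsely reassuring cohort result could be used to discount an SCRI signal.

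**Working it through.** **Plan's own figures.** The protocol gives no figure on infection prevalence, recency or the infection–AESI association, so there is nothing on this point to reproduce. The cohort size is not in dispute. For an upper limit of 3 at 100 per 100,000 person-years, events per arm are 2 × ((1.960 + 0.842)/ln 3)² = 13.01, and 13.01/(0.001 × 60/365) gives the 79,121 in Table 2.

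**Formula.** Section 8.9 proposes three bias parameters for a confounder: its association with the outcome and its prevalence in each arm. Applied here:

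observed IRR / true IRR = [1 + f·r1·(RR − 1)] / [1 + f·r0·(RR − 1)]

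**Inputs (all assumed).**
- f, share of pairs with prior infection: 10% or 20%
- r1, share of prior-infected vaccinees infected in the last 30 days: 1%
- r0, the same share in the prior-infected unexposed: 5–20%
- RR, AESI rate ratio for recent infection: 3–10

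**Acute windows, true IRR = 1.**

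| r0 | RR | f = 10% | f = 20% |
|---|---|---|---|
| 5% | 3 | 1.002/1.010 = 0.99 | 1.004/1.020 = 0.98 |
| 10% | 5 | 1.004/1.040 = 0.97 | 1.008/1.080 = 0.93 |
| 10% | 10 | 1.009/1.090 = 0.93 | 1.018/1.180 = 0.86 |
| 20% | 10 | 1.009/1.180 = 0.86 | 1.018/1.360 = 0.75 |

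These values apply the raised rate to the whole risk window. For the longer windows (28 to 60 days) some dilution is likely, so they lie towards the upper end of the effect for the inputs given.

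**Threshold.** With no recent infection among vaccinees, a 10% downward bias needs a recently infected share p0 of the whole unexposed arm equal to (1/0.9 − 1)/(RR − 1): 2.8% at RR = 5 and 1.2% at RR = 10.

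**Primary 365-day AESIs.** If the excess lasts 30 of 365 days and follow-up is complete, the factor is 1/[1 + p0·(RR − 1)·30/365]. Over p0 = 0.25% to 4.5% and RR = 2 to 30 it runs from 0.9998 to 1/(1 + 0.045 × 29 × 0.0822) = 0.903. Unexposed people are censored at vaccination, so their follow-up may be shorter and the dilution weaker.

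**With recency in the key.** The recently infected share is then equal in the two arms and the factor is 1.

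**The case against.** **The cohort is not primary for acute events.** The SCRI is, and it may carry month-prior infection as a covariate. The cohort is primary only for the four non-acute AESIs, where the bias is small. This stands and limits the reach of the point.

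**Safeguards are planned.**
- Section 8.3.4 says "For the cohort design, covariate status for all time-varying factors will be measured at index date", which can fairly be read to include month-prior infection.
- Section 8.7.1.2 explores other covariates and adjusts for them, or builds a propensity score, where they are imbalanced and predict the outcome.
- Section 8.2.3 plans a subgroup free of COVID-19 at the start of the risk window, censored at infection.

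These help, and could expose the problem. But the first does not explicitly name recent infection for the cohort, the second is conditional, and the third is a subgroup. None changes the matching key or the main comparison with the unexposed.

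**Matching detail is deferred to the SAP.** That is true of the procedure, but 8.7.2.1 already fixes this variable as yes/no.

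**The selection premise is not documented.** The protocol does not say that recently infected people are less often vaccinated. That stands, and the conclusion is conditional on it.

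A reader might also infer a severe distortion in the prior-COVID-19 subpopulation by applying the acute-window formula there. Section 8.7.3 and Table 5 do not support this: that subpopulation is analysed by SCRI for acute AESIs and by cohort only for the 365-day ones. With the excess lasting 30 of 365 days and f = 100%, the formula gives about 0.99 (r0 5%, RR 3: 1.0016/1.0082) to 0.88 (r0 20%, RR 10: 1.0074/1.1479).

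**Conclusion.** The point holds in a limited form. The key permits pairs that differ in recency of infection, and no exclusion prevents them. If recent infection is more common in the unexposed than in vaccinees and raises AESI risk, the IRR against the unexposed is biased downwards.

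In the acute-AESI cohort sensitivity analysis, on the assumed inputs, a true null reads about 0.99 to 0.86 with 10% of pairs previously infected and as low as 0.75 with 20%. For the primary 365-day AESIs the full-cohort bias stayed under about 10% in the scenarios tried, given full follow-up. Active-comparator contrasts should be little affected, because both groups are vaccinated at index.

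A reader might conclude that the design will hide vaccine harm. The documents do not support that: they give none of the inputs needed, the plausible effect starts at negligible, and acute harm is assessed first by the SCRI. The change is still worth making, because it is cheap and repairs the analysis intended to check time-varying confounding.

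**What to change.** For the comparison with the unexposed, replace the yes/no item in 8.7.2.1, 8.1.2.2 and the abstract with three levels at the index date: no recorded infection, recent infection, older infection. The prior month is a natural definition of recent because the SCRI already uses it; the cut-point should be justified. In 8.3.4, name month-prior COVID-19 infection explicitly as a cohort covariate, and report its standardised difference between the matched arms.

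The cost is protocol wording and one changed matching key, using infection dates that the SCRI covariates already require. The downside is that a few vaccinees with a recent infection may find no match; their number should be reported.
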